Study Design: This will be a 6-month (with follow-up, if necessary, to monitor residual implant), open-label, multicenter, adaptive study evaluating the safety, tolerability, and efficacy of 2 formulations of dexamethasone intravitreal implant, AR-1105, in a single eye of up-to 45 subjects between 18 and 80 years of age with macular edema (ME) secondary to retinal vein occlusion (RVO). Since this study represents the first-in-human experience with AR-1105, the study will begin with an initial phase, during which time, up to a maximum of 5 subjects will be treated with AR-1105 clinical formulation 1 (AR-1105-CF1) and followed during weekly visits for up to 2 weeks post-treatment to assess tolerability and safety. Providing none of the subjects experience any clinically-meaningful ocular adverse reactions (possibly) related to treatment with AR-1105 during the initial phase, the study will continue into the randomized phase. During the randomized phase of the study, subjects will be assigned in a 1:1 ratio to either AR-1105-CF1 or AR-1105 clinical formulation 2 (AR-1105-CF2). Data collected from the subjects enrolled into the randomized phase of the study will be primarily summarized separately from subjects enrolled during the initial phase. Treatment will consist of a single intravitreal administration with AR-1105-CF1 or -CF2, each of which has a target dose of 340 µg dexamethasone (2 implants, single injection). During the randomized phase, each treatment group will enroll approximately 20 subjects (i.e. in addition to the enrolled subjects who will participate in the initial phase on AR-1105-CF1). An interim analysis of the first 20 subjects randomized to CF1 or CF2 may be conducted when they have completed 6 months post-treatment to assist in planning future studies. When all subjects in each treatment group have completed their Month 6 visit, the primary safety and efficacy analyses will be conducted. Data collected through Month 6 on the safety and tolerability of each formulation, as well as efficacy signals for each subject randomized, will be used to determine which formulation will be selected for further clinical development. Any subject who presents at Month 6 with visible residual implant will be followed until they require retreatment (following the criteria provided for rescue therapy), or until 1 month after the implant is no longer visible or to Month 9, whichever occurs first. Rescue therapy in the form of standard of care, will be offered to any subject who, in the opinion of the investigator, requires additional therapy for their RVO due to lack of efficacy after Month 3/Week 12. Minimum guideline criteria for considering rescue are an increase in CRT of 50 µm and decrease in BCVA of ≥ 7 letters at any time compared to baseline. In the case of elevated intraocular pressure (IOP) or cataract, investigators should treat the subject according to standard practice. In the case of a cataract, removal should be performed as soon as possible since BCVA could be impacted by the cataract.

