4.1 Method of Assigning Subjects to Treatment Groups

Providing none of the subjects experience any clinically-meaningful ocular adverse reactions (possibly) related to treatment with AR-1105 during the initial phase, the study will continue into the randomized phase. During the randomized phase of the study, subjects will be assigned in a 1:1 ratio to either AR-1105-CF1 or AR-1105-CF2.

5. Sample Size and Power Considerations

This study is not powered to detect a pre-stated efficacy signal, but rather will be used to inform the design and power for future studies. With a sample size of 20 evaluable subjects per treatment group, the study will have 95% confidence of ruling out adverse events (AE) with true incidence rates of 13.9% or higher within each treatment group. That is, with 20 subjects in a treatment group, if an AE of a specific type is not observed, then with 95% confidence, the true incidence rate of that AE is less than 13.9%.

6. Data Preparation

All reported study data will be recorded on the electronic case report forms (eCRF) supplied by Statistic & Data Corporation (SDC). Only the Principal Investigator and authorized study staff according to the Delegation of Responsibilities log are entitled to make entries in the eCRF.

After data are entered into the clinical study database, electronic edit checks and data review will be performed. All data validation specifications and procedures are detailed in the Data Validation Manual as a separate document. When the database has been declared to be complete and accurate, the database will be locked. Any changes to the database after data have been locked can only be made with the approval of the Sponsor and Trial Runners in consultation with SDC.

The final analyses outlined in this document will be carried out after the following have occurred:

- All data management requirements are met according to SDC standard operating procedures, including data entry, performance of edit and validation checks, documentation and resolution of data queries, and database lock with written authorization provided by appropriate SDC and Sponsor personnel.
- Protocol deviations have been identified and status defined (major/minor deviations).
- Analysis populations have been determined.

7. Analysis Populations

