8.4 Data Analysis Conventions

All data analyses will be performed by SDC. Statistical programming and analyses will be performed using SAS® Version 9.4 or higher. Output will be provided in rich text format (RTF) for tables and portable document format (PDF) for tables, listings, and figures using landscape orientation. All study data will be listed by treatment (and phase [initial vs randomized] for CF1), subject and visit (as applicable).

Summaries for continuous and ordinal variables will include the number of observations (n), arithmetic mean, standard deviation (SD), median, minimum, and maximum. Minima and maxima will be reported with the same precision as the raw values; means and medians will be presented to one additional decimal place than reported in the raw values. Standard deviations will be presented to two additional decimal places than reported in the raw values. Summaries for discrete variables will include number and percentages. All percentages will be rounded to one decimal place (i.e., XX.X%). Change from baseline will be calculated as follow-up visit minus baseline.

All statistical tests will be two-sided with a significance level of 0.05 ($\alpha = 0.05$) unless otherwise specified. Confidence intervals for differences between treatment groups will be two-sided at 90% and 95% confidence. All p-values will be rounded to four decimal places; p-values less than 0.0001 will be presented as "<0.0001"; p-values greater than 0.9999 will be presented as ">0.9999."

Unless otherwise specified, summaries will be presented by treatment group and, where appropriate, visit.

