A linear model with change from baseline BCVA letters for study eye only as the response, baseline BCVA letters as a covariate, and treatment group as a main effect will be fit to determine treatment group effect with separate models completed for each follow-up visit. These analyses will be used to determine differences in formulations and may be used to assess whether there are differences in outcomes between subjects' data pre- and post-interim to determine whether the data may be pooled. Subjects who receive rescue medication prior to the summarized visit will have their measure replaced with their last observation prior to receiving rescue medication. The least squares mean, standard error, and CI for each treatment group, and the difference between treatment groups will be presented for

study eye only. Additionally, analyses will be completed using individual two-sample t-tests and 90% and 95% CIs around the difference between treatment groups in mean BCVA and mean change from baseline BCVA for study eye only.

Median time (in months) to achieve a treatment response of ≥ 15 letters improvement from baseline in BCVA for study eye and median time (in months) to rescue therapy will be estimated using Kaplan-Meier methods with 90% and 95% CI, calculated using the method of Brookmeyer and Crowley (1982). The log rank statistic will be used to determine differences in time to achieve response between the two treatment groups to determine differences in formulations. Cox proportional hazards will also be used to analyze time to event, including baseline BCVA as a covariate. Results from unscheduled visits or early termination visits will be included in the time to event analysis.

For the event of achieving a treatment response of ≥ 15 letters improvement from baseline in BCVA for study eye, the starting date will be the date of first dose. Subjects receiving rescue medications prior to or on the same date as the achievement of improvement will be considered censored on the day of rescue medication receipt; subjects with neither rescue medications received nor improvement achieved will be considered censored on the last date known to be rescue medication free and improvement achievement free. For the event of receiving rescue therapy, the starting date for the time to event evaluation will be the date of first dose. Subjects who do not receive rescue therapy will be considered censored on the last date known to be event free.

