Example SAS codes: PROC LIFETEST Data=xxx method=KM;

Strata treatment/test=logrank;

Time AVAL*CENSOR(0);

Run;

where CENSOR indicates censored subjects.

PROC PHREG Data = xxx;

Class Treatment (param=ref ref='CF2');

model AVAL*CENSOR(0) = baseline_BCVA Treatment/ties=exact;

run;

where CENSOR indicates censored subjects.

In all analyses, data from subject visits after receipt of rescue medication will be imputed using last observation prior to receiving rescue medication for continuous endpoints and will be imputed as failures for success/failure variables.

Additionally, a subset of the efficacy analyses will be performed by combining the initial phase subjects with the randomization phase subjects.

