13.2 SD-OCT, FA and FP

CRT measured by Cirrus (Zeiss) or Spectralis (Heidelberg) instrument will be summarized at each visit, using continuous summary statistics including change from baseline. Comparison between treatment groups for CRT will be performed using the same approaches as specified for BCVA in section 13.1.

Two time to event analyses for CRT of study eye as specified below will be evaluated using the same statistical method for the event of achieving a treatment response of ≥ 15 letters improvement from baseline in BCVA in section 12.1. The starting date of the evaluation will be the date of first dose. Results from unscheduled visits or early termination visits will be included in the time to event analysis.

- Time to resolution of macular edema: defined as first time point at which CRT is less than or equal to 315 μm for study eye.
- Time to loss of resolution of macular edema among treatment responders (population for this analysis includes subjects who achieved resolution of macular edema except on the last day of measurement): defined as first time point at which CRT returns to greater than 315 μm from first achieving the resolution of macular edema.

For the event of resolution of macular edema, subjects receiving rescue medication prior to or on the same date as the achievement of resolution of macular edema will be censored on the day of their rescue medication receipt. Subjects with neither rescue medications received, nor resolution of macular edema will be considered censored on the last date known to be rescue medication free and resolution of macular edema free. For the event of loss of resolution of macular edema after resolution achieved, subjects receiving rescue medications prior to the loss of resolution of macular edema will be considered censored on the day of rescue medication receipt and subjects receiving rescue medications on the same date as loss of macular edema will be considered for loss of macular edema. Subjects with neither loss of resolution of macular edema nor rescue medication received will be considered censored on the last date known to be loss of resolution of macular edema free and rescue medication free.

Total area of capillary non perfusion within ETDRS Grid (16DA) and total area of fluorescein leakage within the ETDRS grid assessed by FA using both Optos instruments (i.e ultra-widfield) and non-Optos (i.e widefield) will be summarized using continuous summary statistics.

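### Read literally, the SAP adjusts the Cox model for time to macular-edema resolution for baseline BCVA and does not name baseline CRT, which sets the distance to the 315 µm threshold

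*SAP*

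**What the plan says.** SAP 13.2 adds two CRT time-to-event analyses, which SAP section 17 lists as changes from the protocol. The first is "Time to resolution of macular edema: defined as first time point at which CRT is less than or equal to" 315 µm. The second is time to loss of resolution, in subjects who have already reached that level.

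Neither has its own model statement. Both "will be evaluated using the same statistical method for the event of achieving a treatment response" of at least 15 letters gained, with a pointer to section 12.1. Section 12 is the implant residual assessment and has no subsections. The revision history shows that it was added, so the target is evidently 13.1.

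SAP 13.1 specifies Kaplan-Meier estimates, a log-rank comparison and a Cox model: "Cox proportional hazards will also be used to analyze time to event, including baseline BCVA as a covariate". The example code agrees: "model AVAL*CENSOR(0) = baseline_BCVA Treatment/ties=exact".

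Baseline CRT is measured at screening and at Visit 2, but is not named as a covariate anywhere in the protocol or SAP.

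**The concern.** For a 15-letter gain, baseline BCVA is the natural covariate. For an absolute thickness threshold, the natural covariate is starting thickness. The inclusion criteria set only lower limits on thickness (above 290 to above 320 µm, by sex and instrument) and no upper limit. Some eyes therefore start close to 315 µm and others may start far above it, and thicker eyes will plausibly take longer to reach it or never do so. Baseline BCVA is at best an indirect measure of this.

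With about 20 eyes per arm, a chance difference in mean starting thickness is likely to make the thinner arm look faster, and adjusting for BCVA removes only part of that. The protocol says that efficacy signals will inform which formulation goes forward, so a distorted estimate in this one trial matters even without a confirmatory test.

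**Working it through.** **The plan's own figure.** The only sizing figure is the adverse-event bound of 13.9%. It reproduces as 1 − 0.05^(1/20) = 0.139, and it has no bearing on the Cox models. No hazard ratio, resolution rate, CRT standard deviation or BCVA–CRT correlation is given, so the size of the problem can only be shown over a range.

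**Inputs from the documents.**
- Size: "each treatment group will enroll approximately 20 subjects" (protocol synopsis, Study Design).
- Allocation: "subjects will be assigned in a 1:1 ratio to either AR-1105-CF1 or AR-1105-CF2" (SAP 4.1).
- Tests: "All statistical tests will be two-sided with a significance level of 0.05" (SAP 8.4).
- Primary evaluation period: 6 months (protocol 3.3).

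**Assumed inputs.** About 59% of eyes in the reference arm resolve by Month 6. The log-hazard falls by g per SD of baseline CRT, with g from 0 to 1.5. The correlation of BCVA with CRT is −0.2 to −0.6.

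**Model.** Hazard = λ₀·exp(β·treatment − g·z), where z is standardized baseline CRT and λ₀ = −ln(1 − 0.59)/6 = 0.149 per month. Follow-up is censored at 6 months. There were 6,000 simulated trials per scenario. Each was fitted twice, with treatment plus BCVA and with treatment plus CRT.

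**Cross-check.** With 28 events and HR 2, the Schoenfeld formula gives Φ(√28/2 × ln 2 − 1.96) = Φ(1.834 − 1.960) = 45.0%. The simulated power with CRT in the model, 38–45% over g from 0.4 to 1.5, is consistent with this.

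**How often an imbalance arises.** The SD of the difference in mean baseline CRT is √(2/20) = 0.316 of a between-eye SD. The chance that it exceeds 0.5 SD in either direction is 2 × (1 − Φ(0.5/0.316)) = 11.4%.

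**Results for time to resolution.** Power is at HR 2, and ranges run over the correlations. The gap compares the two models at the same correlation. The HR factor is the multiplier on the estimated HR when one arm is 0.5 SD thicker. Full pass-through is exp(−0.5g), and the share passed is ln(factor)/(−0.5g).

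| g | Power, BCVA | Power, CRT | Gap (points) | HR factor, BCVA | Full pass-through | Share passed |
|---|---|---|---|---|---|---|
| 0 | 43% | 43% | none | – | 1.00 | – |
| 0.4 | 38–41% | 43–45% | about 2–5 | 0.82–0.89 | 0.82 | 58% to nearly 100% |
| 0.7 | 30–34% | 42–44% | about 10 | 0.73–0.83 | 0.70 | 53–90% |
| 1.0 | 26–29% | 40–41% | about 12–15 | 0.69–0.78 | 0.61 | 50–74% |
| 1.5 | 18–22% | 38–39% | about 17–21 | 0.63–0.74 | 0.47 | 40–62% |

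With CRT in the model the HR factor is 0.98–1.03 throughout. Type I error with BCVA adjustment is 4.7–5.6%. At a true HR of 3, the median estimate with BCVA adjustment falls to 2.5–2.7 at g = 0.7 and to 1.9–2.1 at g = 1.5.

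**A different model.** A simulation of monthly thickness readings assumed a median CRT of 480 µm, log-SD 0.30 and correlation −0.35, with 39–51% of eyes resolving. When there was no true effect and one arm was at least 1 SD of the chance imbalance thicker (72 µm on average), the median HR was 0.66 with BCVA and 0.98 with CRT. With a true effect, power was 36% against 46%. This is one assumed scenario and depends on how thinning is modelled. It supports the direction only.

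**Limits.** The tabulated model uses continuous times, without the ties of monthly visits, and has no dropout or rescue censoring. Neither simulation covers loss of resolution.

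**The case against.** **The plan may already mean CRT.** SAP 13.2 names no covariate for these models, and its preceding paragraph says that CRT comparisons follow the approaches set out for BCVA. A reader could substitute the endpoint's own baseline by analogy, and the code is labelled an example. This stands in part: the covariate is inherited through a broken reference and is not written into the CRT models. But the time-to-event paragraph has its own carry-over, to the 15-letter event, and a programmer following it literally would fit baseline BCVA. Under either reading the text needs one clarifying sentence.

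**The consequence is limited.** SAP section 5 says "This study is not powered to detect a pre-stated efficacy signal". Safety is primary, CRT is secondary, and the log-rank comparison is unadjusted whichever covariate is chosen. All of this stands. It limits the weight of the point but does not justify the weaker covariate.

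**Stronger readings that the documents do not support.**
- A reader might infer that the analysis is biased, or that any imbalance carries straight into the hazard ratio. Across randomizations the error rate holds, and within a trial the carry-over varies from partial to nearly complete.
- A reader might infer a definite loss of power. No document figure fixes one, and the loss is zero if baseline CRT is not prognostic.
- A reader might extend the argument to loss of resolution. Every eye in that analysis has already reached 315 µm or less, so baseline CRT is not the distance to the event. The set is also selected after treatment, so chance imbalance between randomized arms does not describe it.

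**Conclusion.** The point holds for the Cox model for time to resolution. On the literal text that model adjusts for baseline BCVA and omits the measurement that fixes the distance to its threshold.

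The harm is to precision, and to the estimate in a trial that happens to be imbalanced. It is not a breach of type I error. Under the assumed inputs, an imbalance of 0.5 SD multiplies the hazard ratio by 0.63–0.89 with BCVA adjustment and by 0.98–1.03 with CRT adjustment. Power at HR 2 falls by nothing to about 20 points, depending on how prognostic baseline CRT is. That strength, the resolution rate and the BCVA–CRT correlation are all assumptions.

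For loss of resolution and for the per-visit linear model of CRT change, naming baseline CRT is a matter of consistency. No error or gain has been shown for either.

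**What to change.** In SAP 13.2:

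1. State that the Cox model for time to resolution contains treatment and baseline CRT in place of baseline BCVA, for example with CRT on the log scale. Use the baseline definition in SAP 8.3, which allows an earlier value when Visit 2 is missing, and do not fix it to Visit 2.
2. Correct the reference from section 12.1 to section 13.1.
3. For consistency, state that the per-visit linear model for CRT change uses baseline CRT.
4. Name baseline CRT for the loss-of-resolution model too, and note that this analysis is in a post-treatment responder subset for which no gain from the change has been shown.

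Baseline BCVA stays for the BCVA endpoints, and the log-rank test is unchanged. A BCVA-adjusted fit may be kept as a sensitivity analysis.

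The cost is a few sentences and one variable name in the code. No new data are needed. Because the study is open-label, the choice should be settled before the analysis.

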3.2 Rationale for Study Design and Control Group

While current treatment options for RVO are effective for many patients, the treatment burden is high. This study is designed to enable selection of the optimal AR-1105 formulation to continue with further clinical development. The optimal formulation will provide strong efficacy and a long duration of effect. The hypothesis is that a longer (>3 months) sustained release should necessitate less frequent intravitreal injections, and a lower steroid dose would potentially result in fewer, or less-frequent steroid-associated AEs without compromising effectiveness. Taken together these attributes would reduce the burden of treatment. The study is designed to inform decisions on further development of AR-1105 as safely and efficiently as possible.

[figure not shown]

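### SAP 13.2 starts the clock for loss of edema resolution at first dose but admits only eyes that later resolve, so a difference in onset can appear as, or mask, a difference in how long resolution lasts

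*SAP*

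**What the plan says.** SAP 13.2 introduces the analyses together: "Two time to event analyses for CRT of study eye as specified below will be evaluated using the same statistical method" as the BCVA response, meaning Kaplan-Meier, log-rank and Cox as set out in SAP 13.1. Before defining either one it states: "The starting date of the evaluation will be the date of first dose". No other sentence in 13.2 sets an origin.

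The first analysis is time to resolution, the first CRT of 315 µm or less. The second is time to loss of resolution, the first later CRT above 315 µm. Its analysis set is restricted: "population for this analysis includes subjects who achieved resolution of macular edema except on the last day of measurement". Its definition adds "from first achieving the resolution of macular edema".

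The example code in SAP 13.1 carries one duration per subject and no entry time. SAP 8.4 sets the test level: "All statistical tests will be two-sided with a significance level of 0.05". Protocol 3.2 explains why duration matters: "The optimal formulation will provide strong efficacy and a long duration of effect".

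**The concern.** An eye enters the second analysis only because it resolved after dosing, yet the stated clock starts at dosing. Between dose and resolution the eye cannot lose a resolution it has not reached. That stretch is immortal time, and it is added in full to the recorded time to loss. Two formulations with the same dry interval but different onset would then have different recorded times.

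This is the SAP's only analysis of how long a response lasts once achieved, and it has its own output (Table 14.2.2.3.2). Time to rescue covers all subjects from dose, and implant visibility is not a response measure. Under Protocol 3.1, efficacy signals through Month 6 feed the choice of formulation, so an onset effect read as durability could colour that choice.

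**Working it through.** **Plan's own figure.** The documents state none for this endpoint. Their only sample-size figure, 13.9%, reproduces as 1 − 0.05^(1/20) = 0.139, but it concerns adverse events with 20 subjects per arm.

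**Identity.** For every responder, time from dose to loss = time from dose to resolution + dry interval. No model is needed.

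| Eye | Resolves (month) | Recurs (month) | From dose | Dry interval |
|---|---|---|---|---|
| A | 1 | 5 | 5 | 5 − 1 = 4 |
| B | 4 | 6 | 6 | 6 − 4 = 2 |

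Eye B is dry for half as long as eye A but has the longer recorded time.

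**Inputs from the documents.** CRT at Months 1 to 6 (SAP 13); responders only (SAP 13.2); log-rank test, no delayed entry (SAP 13.1); two-sided 0.05 (SAP 8.4).

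**Assumptions not in the documents.** 12 responders per arm; dry interval of 1, 2, 3, 4 or 5 months with probabilities 0.20, 0.25, 0.25, 0.20 and 0.10 in both arms, independent of onset; censoring at Month 6; 4,000 trials per row. The faster arm resolves at Month 1 or 2 (80/20), mean 0.8 × 1 + 0.2 × 2 = 1.2 months.

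| Slower arm's onset | Mean | Gap | Rejects, from dose | Rejects, from resolution |
|---|---|---|---|---|
| Months 1/2: 80/20 | 1.2 | 0 | about 5% | about 5% |
| Months 1/2: 50/50 | 1.5 | 0.3 | about 9% | about 5% |
| Months 1/2/3: 30/50/20 | 1.9 | 0.7 | about 22% | about 5% |
| Months 2/3: 50/50 | 2.5 | 1.3 | about 58% | about 5% |

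True dry time is equal in every row. The excess rejections favour the slower arm.

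**Second set of assumptions.** 20 treated per arm, 80% resolving, exponential dry interval with mean 2 months in both arms, mean onset 1.25 months in the faster arm. With mean onset of 1.25, 1.7, 2.3 and 3.3 months in the slower arm, the dose clock favours that arm in 2.8%, 10.4%, 31.8% and 76.8% of 3,000 runs. Typical medians from dose are 3 vs 3, 3 vs 4, 3 vs 4 and 3 vs 5 months (faster vs slower). From first resolution the slower arm is favoured in 2.6% to 3.3%, and medians are 2 vs 2 throughout.

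**If loss follows time since injection.** Set loss at a mean of 4.5 months after injection (SD 1.2, assumed) in both arms.

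- With 12 per arm and the 1.3-month gap, the dose clock rejects in about 5%. The resolution clock rejects in 58%, favouring the faster arm, which really is dry for longer.
- With 20 treated per arm, the dose clock favours the slower arm in only 2.9% to 7.9% of runs, while median dry time is 4 vs 3 months at mean onset 1.7 and 2.3, and 4 vs 2 at 3.3.

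**Delayed entry.** In the 58% scenario, keeping the dose clock but admitting each eye at its resolution date lowers rejection to about 23%, not to 5%. Eyes are still compared at different times since resolution.

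**The case against.** Four points can be made for the plan.

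- **The text is ambiguous.** The wording "from first achieving the resolution of macular edema" can be taken as the origin for this endpoint, and a programmer might do so. This stands: the start-date sentence is the only one that sets an origin, but the definition competes with it. Two derivations are possible, so the SAP needs an edit on either reading.
- **Injection to recurrence may be what is wanted.** The product rationale (Protocol 1 and 3.2) is fewer injections, and on that measure eye B does outlast eye A. This also stands. But a responder-only analysis from dose, without an entry time or its own label, does not deliver that measure cleanly.
- **The size depends on how loss arises.** A reader might infer that the slower formulation will be scored as longer-lasting. The documents do not support that as a general statement. They give no onset data for either formulation, and if loss is tied to time since injection, the dose clock makes the arms look about equal. In that case the resolution clock shows a difference that comes wholly from onset, although the difference in dry time is real.
- **Other outputs help.** Time to resolution is reported alongside with the same methods, and CRT by visit, time to rescue and implant visibility add context. An onset difference would be visible, which lowers the stakes. It does not make the time-to-loss comparison interpretable by itself.

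**Conclusion.** The concern holds as an internal conflict in SAP 13.2 with a predictable consequence. Followed literally, the start-date sentence counts the event-free wait for resolution as duration, and the planned log-rank and Cox comparisons then mix onset with persistence. The arithmetic of that mixing is certain. Its size is not: under the stated assumptions the false-difference rate runs from the nominal 5% with no onset gap to about 58% with a mean gap of 1.3 months, and under wear-off tied to injection the error is concealment of a shorter dry time.

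A reader might also infer that the wrong formulation would be chosen. The documents do not go that far. Selection rests on safety, tolerability and efficacy signals together, and no decision rule attaches to this test. The analysis is secondary, the study is not powered for efficacy (SAP 5), and there is no multiplicity adjustment (SAP 8.5). The issue is interpretation, not the error rate of a primary test. It should be corrected before the analysis is run.

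**What to change.** In SAP 13.2, keep first dose as the start for time to resolution only. For time to loss of resolution, start at the date of that eye's first CRT of 315 µm or less, and align the definition and the start-date sentence. Label the result duration of resolution and report it beside time to resolution, so that onset and persistence are read together.

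If time from injection to loss is also wanted as a retreatment-interval measure, report it separately under that label with delayed entry at the resolution date, and note that delayed entry reduces but does not remove the onset effect.

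The cost is one SAP sentence and one derived date, with no new data. The downside is that reported durations become shorter by each eye's time to resolution, and the result describes dry time, not the interval since injection.
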